7. SAFETY ASSESSMENTS

Patients will be called on a bi-weekly basis to assess for AE/SAEs and worsening symptoms of depression and suicidality throughout the active intervention and once during the 1-month follow-up period.

Suicide risk will be assessed through clinical interview and clinical assessment items on the MINI, BDI, PHQ-9 and CSSR-S. Homicidality, a less common occurrence, will be assessed as per all our clinical trials at the DCRP, through MD or PhD level or supervised psychology intern assessors trained to assess for homicidality on clinical interview. All necessary legal standards, including duty to protect, will be followed in the event of a serious homicidal threat.

Expected AE/SAEs

Heat related side effects could occur, including: cardiac events, cramping, dehydration, fainting, fatigue, heatstroke, light headedness, muscle soreness, nausea, or worsening of hot flashes (for peri – or menopausal women).

7.1 Specification of Safety Parameters

Any abnormalities in psychiatric status, labs, vital signs, ECG, or physical exam on any assessment visit will be assessed for safety. [name] (or his designee) will be responsible for any medical abnormalities, and [name] (or her designee) will be responsible for any psychiatric abnormalities.

7.2 Methods and Timing for Assessing, Recording, and Analyzing Safety Parameters

Please see section above. Any abnormalities will be addressed within a 48 hour workday window.

7.3 Adverse Events and Serious Adverse Events

An **adverse event (AE)** is generally defined as any unfavorable and unintended diagnosis, symptom, sign (including an abnormal laboratory finding), syndrome or disease which either occurs during the study, having been absent at baseline, or if present at baseline, appears to worsen. Adverse events are to be recorded regardless of their relationship to the study intervention.

A **serious adverse event (SAE)** is generally defined as any untoward medical occurrence that results in death, is life threatening, requires inpatient hospitalization or prolongation of existing hospitalization, results in persistent or significant disability/incapacity, or is a congenital anomaly.

Any abnormal (outside the normal range) liver function values or thyroid values will be followed up on and if necessary referred for appropriate clinical care.

AEs that will be solicited on bi-weekly phone call (Bi-Weekly Phone Monitoring Form) will be: depression, suicidality, muscle soreness, or AEs/SAEs.

Unsolicited events will be captured during bi-weekly phone calls (Bi-Weekly Phone Monitoring Form) or during assessment visits (Adverse Events Form).

Reporting procedures are described in section 7.4 below.

7.4 Reporting Procedures

The PI will be responsible for the reporting of any SAEs or AEs to the IRB, DSMB, and NCCIH as necessary. Study-related adverse events will be reported to the IRB and NCCIH as soon as they are discovered by any study staff member and discussed with PI or designee (within 24 hours). AE and SAE reports and annual summaries will not include subject- or group-identifiable material. Each report will only include the identification code. Other adverse events will be reported following the rules of the Partners IRB. Short-term elevations in participant distress are not considered adverse events.

SAEs that are unanticipated, serious, and possibly related to the study intervention will be reported to the mentorship team, Independent Monitors, IRB, and NCCIH in accordance with requirements.

Unexpected fatal or life-threatening AEs related to the intervention will be reported to the NCCIH Program Officer within 7 days. Other serious and unexpected AEs related to the intervention will be reported to the NCCIH Program Official within 15 days.

Anticipated or unrelated SAEs will be handled in a less urgent manner but will be reported to the IRB, NCCIH, and other oversight organizations in accordance with their requirements.

7.5 Follow-up for Adverse Events

Subjects will continue to be monitored for safety after an AE/SAE has occurred until the issue has resolved or is considered stable. Subjects will be called or asked to come in to assess AE/SAEs if determined necessary by study clinician.

7.6 Safety Monitoring

A data safety monitoring board (DSMB) has been assembled prior to the start of the study. The board consists of three staff-level investigators who are not key personnel involved with this grant. They are qualified to review the patient safety data generated by this study. One has expertise in mind-body interventions ([name], PhD); the second has expertise in clinical trial design ([name]); the third has expertise as a statistical consultant ([name]). The DSMB will meet at least quarterly per year to review study progress, address any difficulties with recruitment, and address any safety related matters that may arise. Details of the logistics of the DSMB are as follows:

- a. Unblinded Reporting** – Safety information for this study will be reported to the DSMB in an unblinded manner. A statistical penalty will not be assessed for the ongoing unblinded review of safety by the DSMB. Unblinded data will not be released to the investigators unless necessary for safety reasons.
- b. Range of Safety Reporting to the DSMB** – It is considered necessary for the purpose of monitoring the safety of the study that the DSMB review not only AEs and SAEs, but other data that may reflect differences in safety between treatment groups. This

includes treatment retention rates, reasons for drop-out, and laboratory values reflecting potential danger to patient.

- c. **Serious Adverse Events** – Expedited review will occur for all events meeting the FDA definition of SAEs. This also includes any event that a study investigator or the DSMB judges to impose a significant hazard, contraindication, side effect, or precaution.
- d. **Non-Serious Adverse Events** – At periodic intervals (quarterly during the course of the study and then again at its completion), the DSMB will be provided with un-blinded summaries of the numbers and rates of adverse events by treatment group. These reports will include types of events, severity, and treatment phase. Data on individual non-serious adverse events is not expected to be needed for this review.
- e. **Other Safety-Related Reports** – At twelve-month intervals throughout the course of the study, the DSMB will also receive unblinded summary reports of treatment retention and reasons for drop-out, by treatment arm and study phase.
- f. **Study Stopping Rules** – If at any time during the course of the study, the DSMB judges that risk to subjects outweighs the potential benefits, the DSMB shall have the discretion and responsibility to recommend that the study be terminated.

8. INTERVENTION DISCONTINUATION

If a subject's overall depressive symptoms significantly increase, or if a subject develops suicidal intent, he/she will be evaluated by a study clinician to determine if referral for clinical intervention is needed. This will be determined per study clinician judgment.

- Subjects who demonstrate an increase in the IDS total score of 25% or greater over baseline or whose QIDS-C score is a >16 (indicating severe depression) will be assessed for referral to evidence-based clinical treatment.
- A “yes” on items 4 or 5 on the Columbia-Suicide Severity Rating Scale, a score of 3 on the suicidal ideation question of the QIDS-C, or a score of 3 on the IDS-CR suicide item will prompt assessment, and if necessary, appropriate referral.
- If a subject reports that worsening severity is due to situational factors and there appears to be no acute risk of self harm or other significant worsening, they will be given the option to be reassessed within 72 hours (most likely via phone) to determine the safety of continuation.
- Patients will also be dropped from the study if they are, in the judgment of the study clinician, deemed to be a safety risk, the intervention appears to making their condition worse, or if new information is uncovered re: an untreated condition (e.g., onset of substance abuse or physical condition) that would affect participation or threaten the integrity of the study.

Disconsolation due to Non-Adherence: if a subject does not attend a yoga session for two weeks, he or she will be discontinued from the intervention – though he or she will be asked to come in for a final assessment visit. If a subject misses more than two consecutive assessment visits, he or she will also be discontinued from the intervention, unless there are extenuating circumstances communicated to the study team. Subjects will be allowed to continue if they are only attending one yoga class during any specified week, though this will be controlled for in analyses – their data will still be useful. If subjects are discontinued from the intervention, they will be included in the modified ITT (MITT) analyses (see section 9 below) and invited for a Visit 6 (final exit visit).

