6.2.5 Completion/Final Evaluation

Visit 6: Study Primary Endpoint (Week-8) for IYG and DYG (repeated for DYG in Visit 11 as 9-week Yoga Assessment)/Early Discontinuation Visit – IYG and DYG

- Physical Examination
- Habits Questionnaire
- C-SSRS since Last Visit
- IDS-CR
- HAM-D-28
- Self-Sated Questionnaires (STAI, SF-36, Q-LES-Q, EIFI, PSS, PSQI, FFMQ, RRS, URICA)
- Concomitant Medications
- Vital Signs
- Waist-to-Hip Ratio
- Physiological Markers (i.e., inflammatory markers [blood], cortisol [saliva])

- Collect Sleep Diary (can bring to the following visit as long as it was completed for the right week)
- Adverse Events
- Hot Yoga Beliefs Scale
- Acceptability Interview (completed at Visit 11 for DYG)
- MINI Mood Module

Final Evaluation: 1-Month Follow-Up Post-Yoga Visit – IYG (Visit 7) and DYG (Visit 12)

- Physical Examination
- Habits Questionnaire
- C-SSRS since Last Visit
- IDS-CR
- HAM-D-28
- Self-Rated Questionnaires (STAI, SF-36, Q-LES-Q, EIFI, PSS, PSQI, FFMQ, RRS)
- Concomitant Medications
- Vital Signs
- Waist-to-Hip Ratio
- Physiological Markers (i.e., inflammatory markers [blood], cortisol [saliva])
- Collect Sleep Diary
- Adverse Events
- Hot Yoga Beliefs Scale
- MINI Mood Module

Potential Reasons for Early Termination

Subjects can be potentially dropped from the intervention due to: 1) adherence to yoga or assessment visits, 2) being deemed unsafe to continue the yoga intervention, 3) worsening of depressive symptoms, or 4) suicide risk.

Please see section 8 (Intervention Discontinuation) for operational definitions of the above.

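### Section 8 leaves IDS-CR follow-up after stopping undefined: study or intervention, and early exit visit or week 8

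*Combined protocol and SAP*

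**What the plan says.** Section 8 removes some participants outright: "Patients will also be dropped from the study if they are, in the judgment of the study clinician, deemed to be a safety risk". It adds two further grounds: "the intervention appears to making their condition worse, or if new information is uncovered re: an untreated condition".

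Section 6.2.5 uses the other word on overlapping grounds: "Subjects can be potentially dropped from the intervention due to" reasons that include "being deemed unsafe to continue the yoga intervention, 3) worsening of depressive symptoms, or 4) suicide risk". It then sends the reader on: "Please see section 8 (Intervention Discontinuation) for operational definitions of the above". Section 5.3.1 also speaks of stopping the intervention, at the clinician's discretion, for worsening depression or safety issues.

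On follow-up, section 8 says that a participant stopped for two weeks without yoga is not simply released: "he or she will be asked to come in for a final assessment visit". More generally: "If subjects are discontinued from the intervention, they will be included in the modified ITT (MITT) analyses", and they are "invited for a Visit 6 (final exit visit". Section 6.2.5 gives Visit 6 two roles in one title, the week-8 primary endpoint and the early discontinuation visit, for both arms. Its list of assessments includes the IDS-CR.

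Section 9.3 puts anyone with one post-baseline visit in the MITT, and requires a week-8 visit of a completer. Hypothesis 1a asks that 75% of each group have a week-8 assessment.

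**The concern.** The section cited for the definitions uses a different word from the section that cites it. Two coordinators could handle the same event differently: one ends all contact, the other stops yoga and books an exit visit.

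Beneath the wording is a gap that either word leaves open. No sentence says that the remaining scheduled IDS-CR visits continue, and none says when the single exit visit is held. Because Visit 6 carries both labels, a rating taken at an early exit can be filed as the week-8 rating. Otherwise the week-8 rating may never be taken. Several of these exits are tied to outcome, since worsening and suicide risk are among the grounds.

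The stakes are the pilot's own aims. Section 9.2 says the main purpose is to estimate an effect size for a larger trial, and retention is Primary Aim I. Both rest on knowing what counts as a week-8 rating.

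**Working it through.** **The plan's own figures.** Section 9.2 gives 79% power at d = 0.70 and 50% at d = 0.50, for a two-sided t-test at 0.05 with 32 per arm. Recomputed with the noncentral t: 78.7% and 50.4%, so they reproduce. The standard error of d is about sqrt(2/32) = 0.25. With 30 per arm, power at d = 0.70 is 76.0%, so loss of power is not the main issue.

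**Retention.** 75% of 40 is 30, so each arm can lose 40 - 30 = 10 week-8 visits (if all 40 have a post-baseline visit, which section 9.6 makes the definition of enrollment).

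**One event, four records.** Take a participant stopped just after the week-3 visit. All four readings keep the participant in the MITT, because scores already recorded stay in.

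| Reading | Week-5 IDS-CR | Week-8 IDS-CR | Completer (9.3) | Retained (1a) |
|---|---|---|---|---|
| Removed from study, no exit visit | none | missing | no | no |
| Visit 6 at exit, filed as exit only | none | missing | no | no |
| Visit 6 at exit, filed as week 8 | none | an early rating | yes | yes |
| Visit 6 held at week 8 | none stated | true week-8 rating | yes | yes |

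**Symmetry.** The DYG starts yoga only after Visit 7 (6.2.2), so before crossover the two-week non-attendance rule can stop only IYG participants. The safety and missed-visit rules can be met in either arm.

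**Size, for illustration.** The documents give no drop rate, so every input here is assumed:
- simulation of 400,000 per arm, with IDS-CR at baseline and weeks 1, 3, 5 and 8, multivariate normal with constant correlation 0.4 or 0.6;
- SD of change 8, 10 or 12; baseline mean 30 or 35, with entry above 23;
- linear mean change, -3 points at week 8 in controls, and a yoga benefit of 0.65 SD;
- removals drawn from patients at least 25% above baseline, with the chance set so that 5% or 10% of the IYG (2 or 4 of 40) are removed, or all who meet the trigger if fewer than 10% do.

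Bias = (estimated benefit - full-data benefit) / SD of change; positive favours yoga. Removed patients have no week-8 rating. In the rated case they leave after the visit that shows the rise. In the unrated case they leave before it, with no exit rating.

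| Removals | Worsening rated? | Completer analysis | Mixed model |
|---|---|---|---|
| IYG only | yes | +0.031 to +0.087 | within 0.001 of 0 |
| IYG only | no | +0.042 to +0.111 | +0.019 to +0.053 |
| Same chance, both arms | yes | -0.006 to -0.027 | within 0.001 of 0 |
| Same chance, both arms | no | -0.028 to -0.107 | -0.017 to -0.065 |

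The completer bias crosses zero when a worsened DYG patient's chance of removal is 0.78-0.86 (rated) or 0.53-0.63 (unrated) of a worsened IYG patient's.

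**Misfiling.** In the rated, IYG-only case, suppose the rating that prompted removal stands in for week 8. The completer bias then changes sign, to between -0.08 and -0.18 SD, because a poor early score enters the yoga arm as its endpoint. A fresh rating at exit gives a smaller shift of the same sign.

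**The case against.** Context goes a long way to settle the wording. Section 8 is titled for intervention discontinuation, section 6.2.5 cites it for that purpose, and the early discontinuation label on Visit 6 is not limited by reason. One exit IDS-CR for everyone who stops is the likelier reading. A reader might infer that participants removed for safety get no further rating at all, or that no reading yields a week-8 rating. The documents support neither inference: an exit visit probably applies, and since Visit 6 is also the week-8 visit, a rating at week 8 is possible. What stands is that its timing is unstated and that the visits in between are not continued.

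The simulated trigger is not the removal rule. In section 8 a 25% IDS rise leads to assessment for referral. Removal is a separate clinical judgement, and worsening put down to circumstances can be reassessed within 72 hours. Some grounds, such as a new physical condition, need not track the IDS-CR. This stands, and it is why the sizes are illustrations only.

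The likelihood-based mixed model copes well when the worsening was rated first. That stands too, provided an exit rating is not entered as week 8. It does not cover every case. Section 8 also acts on the QIDS-C, which is collected on calls between visits, so a patient can be removed before any IDS-CR shows the change. Section 9.6 plans to test whether data are missing at random and otherwise promises unspecified advanced methods. Those cannot recover ratings that were never taken.

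Finally, ratings made after other care has begun answer a different question from the effect of yoga alone. That is fair, and it is the price of the fix.

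**Conclusion.** The point holds as a gap in the follow-up rules with a cheap remedy. It does not invalidate the primary analysis. The wording conflict is real but probably a slip. The firmer defect is that no text continues the IDS-CR after stopping, or says whether an early Visit 6 counts as week 8.

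The effect is probably small. Under the assumptions shown, the completer analysis moves by at most about 0.11 SD either way (about 1.1 IDS-CR points) when leavers have no week-8 rating. The mixed model moves by about zero if worsening was rated, and by up to about 0.065 SD if it was not. All are well below the standard error of 0.25 SD. The Hypothesis 1a count is affected directly: depending on the reading, the same person is one of the ten losses allowed or is retained.

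A reader might infer a bias in favour of yoga, since only the IYG can be made worse by yoga before crossover. The documents do not support a direction. Safety removals apply to both arms, worsened patients would be commoner on the waitlist if yoga works, and misfiled exit ratings push the other way.

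**What to change.** In section 8, replace removal from the study with discontinuation from the intervention; for the DYG before Visit 7, say that yoga will not be started. Then state:

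- After any discontinuation, including for non-adherence, the blinded IDS-CR continues in both arms at the remaining scheduled visits through week 8 from baseline, by phone if needed, unless consent is withdrawn or the assessment itself would be unsafe.
- An early exit visit does not count as the week-8 assessment for the endpoint, for completer status or for retention.
- The date and reason for stopping, and the start date of any new treatment, are recorded.

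The clinician's authority to stop yoga is unchanged. The cost is a few sentences and a few ratings that are already scheduled; section 6.2.4 already allows clinician ratings by phone. Section 7.6 already gives the DSMB drop-out reasons by arm, so no new report is needed. The downside is that a few ratings will follow the start of other care, so the estimate reflects assignment to yoga whatever care came later. Some patients will still decline or be unfit to be rated.

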Bikram Yoga Research: While there is no literature on Bikram Yoga for depression, several studies of Bikram Yoga demonstrate improvements in physiological and psychological processes implicated in depression. **Physiologically:** In a recent 8-week pilot trial, 3 weekly

Bikram Yoga classes improved glucose tolerance in 15 older obese adults compared to 14 young lean subjects. This supports Bikram Yoga as a therapeutic tool for metabolic dysfunction²⁹, and depression is associated with metabolic disorders³⁰. Another study found that 8 weeks of 3 weekly Bikram Yoga classes improved arterial stiffness in 24 younger adults (30±1 years), and significantly reduced insulin resistance in 18 older adults (53±2 years)³¹. The relationship between depressive and anxiety disorders and early markers of arterial stiffness³², indicates a common pathophysiology with depression. **Psychologically:** In an uncontrolled study of 54 healthy individuals, Bikram Yoga improved mindfulness and decreased stress³³, suggesting benefits in depression via effects on mindfulness and perceived stress. In an unpublished dissertation, DeBoer et al.³⁴ reported preliminary completer data of twice weekly Bikram Yoga classes (n=27) versus a waitlist control (n=25) for women (ages 25-45) with stress-induced eating and high perceived stress. This study demonstrated a dropout rate of 11.5%, lower than in most depression trials. The 4 subjects who discontinued yoga did so in the initial stages of the practice. This study provided preliminary evidence of the acceptability of recruiting and retaining a psychiatric population for this intervention. The effect size for the change in the Beck Depression Inventory (BDI-II)³⁵, based on Cohen's *d*, was medium (0.54), suggesting an advantage for Bikram Yoga over the waitlist. As this study did not require depressive symptoms for entry, the effect size for depression in the proposed study will likely be higher. The Beck Anxiety Inventory (BAI)³⁶ demonstrated a large effect for Bikram Yoga over control (*d*=1.19). There were also large effects for Bikram Yoga's ability to reduce scores on the Ruminative Responses Scale (RRS)³⁷ (.76), the Perceived Stress Scale (PSS)³⁸ (.83), and the Response to Positive Affect Scale³⁹ (.76). I will include the PSS and RRS in our study as secondary outcome measures, due to these results.

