3. STUDY DESIGN

The project is an acceptability, feasibility, and pilot efficacy trial of hyperthermic yoga vs. a waitlist control for 80 adults with at least mild depressive symptoms. The target enrollment for the study will be 160 to properly screen the number of needed randomized participants. The hyperthermic yoga intervention will take place in two community Bikram Yoga studios in the Boston area. Bikram Yoga Boston is owned by [name] and Bikram Yoga Cambridge is owned by [name]. Participants will attend classes at either of these studios, free of charge – i.e., the intervention will be community-delivered. Participants will be asked to attend

at least two weekly 90-minute Bikram Yoga classes during the 8-week intervention phase of the study. All research related assessments will take place at the Depression Clinical and Research Program (DCRP) at the Massachusetts General Hospital (MGH). The enrollment period for participants will depend upon the arm to which they are randomized: 1) immediate yoga group (IYG) will complete the protocol in approximately 15 weeks; and 2) the control or delayed yoga group (DYG) will complete the protocol in approximately 24 weeks.

Retention Strategies: Patients with depressive symptoms frequently have impaired motivation. In the only known RCT of hyperthermic yoga for a psychiatric population, subjects who dropped out tended to do so after 1-2 sessions. Most who got through this critical period completed the study³⁴. To address this: 1) study staff, the PI or designee, will administer a 50-minute pre-yoga baseline psychoeducation session with a preparatory handout, which they take home with them. 2) Participants will receive a bi-weekly telephone call from the PI, and when not available, another study staff member.

Subject Remuneration: Subjects in the DYG will be compensated for their time during the waitlist period (\$25 for baseline; week 1, 3, 5 and 8; total=\$125) to encourage participation. Subjects in IYG will only be paid for the 1-month follow up visit (\$25), as they will receive free yoga classes at the outset of the study. All subjects will receive \$30 per cortisol assessment.

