6.2.4 Follow-up Visits

Phone visits will occur bi-weekly from baseline through the end of the study intervention period. During the 1 month follow-up period, there will be a phone call during the midpoint (2-weeks into the follow-up period).

Assessment visits will be completed within a reasonable time frame (+/- 3 workday window), but may occur outside this window if deemed appropriate by study staff.

Visit 3 (Week-1 Assessment)* – IYG and DYG

- IDS-CR
- Self-Rated Questionnaires: STAI, SF-36, Q-LES-Q, EIFI, PSS, PSQI, FFMQ, RRS
- Concomitant Medications
- Vital Signs⁺
- Adverse events

Visit 4 (Week-3 Assessment)* – IYG and DYG

- IDS-CR
- Self-Rated Questionnaires: STAI, SF-36, Q-LES-Q, EIFI, PSS, PSQI, FFMQ, RRS
- Concomitant Medications
- Vital Signs⁺
- Give salivettes
- Give Sleep Diary (can bring to the following visit as long as it was completed for the right week)
- Adverse Events

Visit 5 (Week-5 Assessment) – IYG and DYG

- C-SSRS since Last Visit
- IDS-CR
- Self-Rated Questionnaires: STAI, SF-36, Q-LES-Q, EIFI, PSS, PSQI, FFMQ, RRS
- Concomitant Medications
- Vital Signs
- Waist-to-Hip Ratio
- Physiological Markers (i.e., inflammatory markers [blood], cortisol [saliva])
- Give salivettes
- Collect and give Sleep Diary (can bring to the following visit as long as it was completed for the right week)
- Adverse Events

Visit 8 (Week-1 Yoga Assessment) – DYG

- IDS-CR
- Self-Rated Questionnaires: STAI, SF-36, Q-LES-Q, EIFI, PSS, PSQI, FFMQ, RRS
- Concomitant Medications
- Vital Signs⁺
- Adverse Events

Visit 9 (Week-3 Yoga Assessment) – DYG

- IDS-CR
- Self-Rated Questionnaires: STAI, SF-36, Q-LES-Q, EIFI, PSS, PSQI, FFMQ, RRS
- Concomitant Medications
- Vital Signs⁺
- Give salivettes
- Give Sleep Diary
- Adverse Events

Visit 10 (Week-5 Yoga Assessment) – DYG

- C-SSRS since Last Visit
- IDS-CR
- Self-Rated Questionnaires: STAI, SF-36, Q-LES-Q, EIFI, PSS, PSQI, FFMQ, RRS
- Concomitant Medications
- Vital Signs
- Waist-to-Hip Ratio
- Physiological Markers (i.e., inflammatory markers [blood], cortisol [saliva])
- Give salivettes
- Collect and give Sleep Diary (can bring to the following visit as long as it was completed for the right week)
- Adverse Events

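### IDS-CR ratings of participants who stop yoga appear to end at an early Visit 6, so week-8 scores may be lost mainly in the immediate yoga group; continuing the ratings to week 8 is a cheap improvement

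*Combined protocol and SAP*

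**What the plan says.** Section 8 discontinues from the intervention anyone who goes two weeks without a class, "though he or she will be asked to come in for a final assessment visit". It then states of discontinued participants that "they will be included in the modified ITT (MITT) analyses (see section 9 below) and invited for a Visit 6 (final exit visit". It also has a separate category: "Patients will also be dropped from the study if they are, in the judgment of the study clinician, deemed to be a safety risk".

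Section 6.2.5 gives one heading and one assessment list, including the IDS-CR, to two purposes: "Visit 6: Study Primary Endpoint (Week-8) for IYG and DYG (repeated for DYG in Visit 11 as 9-week Yoga Assessment)/Early Discontinuation Visit". Section 6.2.4 allows three workdays either side of a scheduled visit, "but may occur outside this window if deemed appropriate by study staff".

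Under section 9.3 the MITT needs one post-baseline visit, while a completer needs a week-8 visit. Hypothesis 1a also refers to week 8. Section 9.6 plans a likelihood-based mixed model with a test of time by condition. It does not say whether time means the nominal visit or the elapsed week. Section 9.2 says the pilot's main purpose is to estimate an effect size.

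In both schedules (6.1.1 and 6.1.2) V6 carries a triple-asterisk footnote. Its text is not in the copy reviewed.

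**The concern.** No section that can be read fixes when the exit visit takes place or the study time at which its IDS-CR score is analysed. Calling the visit final, and listing it as an early discontinuation visit, suggests that it follows soon after stopping and that ratings then cease.

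Before crossover only the IYG is attending classes, so the non-attendance trigger can sensibly act only there. The other triggers (missed assessments, worsening, safety) can act in both arms. Lost week-8 scores would therefore fall mainly in the IYG, among people who remain in the MITT, and would bear on the effect estimate that the pilot exists to produce.

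There is also a small inconsistency after crossover. Section 8 sends every discontinued participant to Visit 6, whereas section 6.2.5 gives Visit 11 as the end visit of the DYG yoga phase.

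**Working it through.** **Plan's own figure.** Section 9.2 gives 79% power at d = 0.70 and 50% at d = 0.50 (32 per arm, two-sided 5% t-test). A noncentral t calculation gives 78.7% and 50.4%, so these reproduce. They are used here only as the source of d = 0.70 and of 32 per arm.

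**When exits would fall.** Section 3 says of the earlier trial that "subjects who dropped out tended to do so after 1-2 sessions". Section 2.2 agrees: "The 4 subjects who discontinued yoga did so in the initial stages of the practice". At two classes a week, one or two sessions fall in week 1. Two weeks of absence then puts exit at about weeks 2-3, five to six weeks before the endpoint.

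**How many.** Section 2.2: "This study demonstrated a dropout rate of 11.5" per cent. The four who stopped yoga are 4/27 = 14.8% of that arm, or 4/31 = 12.9% if the 27 are completers only. Of 40 in the IYG: 40 × 0.115 = 4.6 and 40 × 0.148 = 5.9, so about 5 to 6 people.

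**Case A: the early score stands in for week 8.** These assumptions are not in the documents:
- change is linear over 8 weeks;
- natural improvement by week 8 is N = 0, 0.25 or 0.5 SD;
- the yoga benefit at exit week w is b = 0.70 × w/8;
- that benefit is fully kept (k = 1) or fully lost (k = 0) by week 8.

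With a share f of the IYG stopping, the shift in the week-8 difference is f × [(N × w/8 + b) − (N + k × b)] = f × [(1 − k) × b − N × (1 − w/8)]. A positive value overstates the yoga effect.

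- Lowest at w = 2, N = 0.5, k = 1: −0.375f.
- Highest at w = 3, N = 0, k = 0: +0.2625f.

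| f | lowest | highest |
|---|---|---|
| 0.115 | −0.043 | +0.030 |
| 0.129 | −0.048 | +0.034 |
| 0.148 | −0.056 | +0.039 |

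High scenario, f = 0.25 with exits as late as week 5: −0.375 × 0.25 = −0.094, up to 0.4375 × 0.25 = +0.109.

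**Case B: week 8 is missing.** Suppose every stopper loses all benefit and earlier scores do not predict this. A missing-at-random estimate then overstates the effect by f × 0.70 = 0.081 (f = 0.115) or 0.104 (f = 0.148). At an assumed 25% it is 0.25 × 0.70 = 0.175. If earlier scores do predict the loss, there is no bias.

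**Yardstick.** The standard error of d with 32 per arm is about √(2/32) = 0.25. All Case A values, and the Case B values at the rates taken from section 2.2, are below half of that (0.125).

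**Retention.** Five to six exits leave 35/40 = 87.5% or 34/40 = 85% at week 8, against the 75% goal.

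**The case against.** **Visit 6 may simply be held at week 8.** Section 8 sets no date for the exit visit. It separates stopping the intervention from being dropped from the study, and the visit it names is the week-8 visit. The unseen footnote sits on exactly this visit. This stands. A reader might infer that the plan must either misplace an early score or lose the week-8 score, and the documents do not go that far. The wording favours an early visit without requiring one.

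**The mixed model largely copes.** It keeps all MITT participants, uses weeks 1, 3 and 5, and could use actual time. That would deal with mistiming. It would not recover week-8 scores that were never collected, and section 9.6 names no method for data that are not missing at random. The HAM-D-28 has no rating between baseline and Visit 6 to lean on.

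**The sizes are illustrative.** The formula is a plain week-8 contrast, assumes that every stopper attends the exit visit, and ignores DYG exits. If 11.5% means 6 of 52 (an assumption), two of 25 controls also left. With the same exit timing, they offset 0.08 × 0.375 = 0.030, and −0.056 becomes about −0.026. This stands, and it makes the effect smaller.

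**Two stronger readings fail.**
- One could compute d = 0.57 to 0.67 and power of 61% to 76% by mislabelling 10% to 25% of IYG scores. That credits people who stopped at weeks 2-5 with the full 0.70 at week 8, which nothing in the documents supports.
- One could suspect an inflated retention result. Hypothesis 1a and the completer definition both say week 8, so on their plain wording an early exit does not count.

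**Continued rating goes beyond cleaning up a label.** True. It is offered as an improvement to the design.

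**Conclusion.** The shared Visit 6 label is explicit, and no readable section fixes the timing of an early-exit IDS-CR. On the natural reading, week-8 scores of about 5 to 6 of 40 IYG participants would go uncollected, with no matching loss from non-attendance in the DYG before crossover.

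The expected effect on the estimate is small and can go either way: about −0.06 to +0.04 SD if an early score is substituted, or up to about 0.10 SD overstatement if week 8 is missing. These figures rest on one earlier trial's stopping rate and on assumed trajectories. The retention goal and the power calculation are not in doubt. If the V6 footnote already sets the timing, the coding part falls away. The continued ratings would then still matter wherever the visit is held before week 8, and the Visit 6 / Visit 11 wording would still need reconciling.

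**What to change.** Leave the yoga-stopping rules and the MITT unchanged.

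**Main change.** In both arms, ask participants who are discontinued from the intervention, and who have neither withdrawn consent nor been dropped from the study, for the blinded IDS-CR at the remaining scheduled weeks through week 8 from randomisation. Ask for the rating alone, by phone if needed. Section 6.2.4 already allows clinician ratings by phone in extenuating circumstances but ties other visits to a blood draw, so its text needs extending to these rating-only contacts.

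**Supporting clarifications.** Give an early exit visit its own code, analyse it at its actual study week, and count it as week 8 only if it falls within a stated week-8 window. Reconcile sections 6.2.5 and 8 on the exit visit for DYG participants who stop during their yoga phase. That last item is minor and outside the primary analysis.

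**Cost.** A short text change, one visit code and some phone ratings. An exit at week 2 leaves three scheduled ratings (weeks 3, 5 and 8) and an exit at week 3 leaves two, so 5 × 2 = 10 to 6 × 3 = 18 calls for the IYG. Section 5.2 describes the blinded assessors as available without extra cost. Some participants will decline, and week-8 blood markers for those who stopped will stay missing.
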